1 PROTOCOL SUMMARY

1.1 SYNOPSIS

| | |
|---|--|
| Title: | SHARE: Sharing Healthcare Wishes in Primary Care |
| Grant Number: | R01AG058671 |
| Study Description: | This study will test a multicomponent communication intervention, referred to as SHARE, to proactively engage family members or friends (interchangeably referred to as “family” and/or “caregiver”) and support advance care planning in primary care. We will conduct a two-group randomized trial at up to 10 primary care practices in which 124 dyads (+/- 10) will receive a control protocol of minimally enhanced usual care and 124 dyads (+/- 10) will receive the SHARE protocol. We test the efficacy of SHARE on quality of communication (primary outcome) and advance care planning processes (secondary outcomes) at 6 months among primary care patients with cognitive impairment (mild-severe) and family caregiver dyads. For patients who die by 24 months, we examine the quality of end of life care and bereaved family caregiver experiences with medical decision-making (secondary outcomes). |
| Objectives: | To test the efficacy of SHARE on improved quality of communication (primary outcome) and end-of-life experiences (secondary outcomes) of primary care patients with cognitive impairment (mild-severe) and family caregivers. |
| Endpoints: | Primary Endpoint: Quality of Communication and Quality of End of Life Care Secondary Endpoints: Advance care planning processes and bereaved family caregiver experiences with medical decision-making |
| Study Population: | We plan to enroll a sample of 248 (+/- 20) person-family dyads comprising primary care patients with cognitive impairment ages 80 years or older and the person who helps them the most with medical decision making, who we refer to as their caregiver. This study focuses on persons ages 80 and older with cognitive impairment (mild-severe) . |
| Stage: | Stage 1 Behavioral Intervention |
| Description of Sites: | We will conduct the trial at up to 10 primary care practices within two health systems (Johns Hopkins Community Physicians, and MedStar Health System) in the Baltimore/Washington area. |
| Description of Study Intervention/Experimental Manipulation: | SHARE encompasses the following four therapeutic elements: 1) a letter from the practice introducing the initiative, 2) access to a designated person (medical assistant, social worker, nurse, or lay person) trained to lead advance care planning discussions, 3) person-family agenda-setting to align perspectives about the role of the caregiver and stimulate discussion about goals of care, and 4) education about communication and available resources. |
| Study Duration: | The project period extends over four years. |
| Participant Duration: | Participants in both groups will be followed over a 24-month period. |

1.2 SCHEMA

1.3 SCHEDULE OF ACTIVITIES

| Assessment | Screening Visit Day -30 to Day -1 | Enrollment Day 1 | Randomize | ACP, Patient Portal Use | 6 Months Day 182 (±30 Days) | 12 Months Day 365 (±30 Days) | 24 Months Day 730 (±30 Days) | Bereavement Survey 60 to 90 Days After Death |
|---|---|---------------------|-----------|----------------------------------|--------------------------------------|---------------------------------------|---------------------------------------|---|
| Oral consent | X | | | | | | | |
| Informed consent | | X | | | | | | |
| Patient characteristics * | | X | | | X | X | X | |
| Family characteristics & caregiving circumstances * | | X | | | X | X | X | |
| Primary care interactions * | | X | | | X | X | X | |
| Intervention processes * | | | | X | | | | |
| Patient, Family experiences * | | X | | | X | X | X | |
| Outcomes at the end of life * | | | | | | | | X |
| Alert Events ** | X | X | | | | | | |
| Adverse Events ** | | X | X | X | X | X | X | X |
| | Note: Enrollment visits and ACP discussions are in-person or remote. All other contacts involve telephone or electronic contacts. *See Section 9 for description of measures that are assessed. ** Section 8 for description of alert and adverse events. | | | | | | | |

2 INTRODUCTION

2.1 STUDY RATIONALE

Advance care planning is a process that supports adults at any age or stage of health in understanding and sharing their personal values, life goals, and preferences regarding future medical care.¹ Early initiation of advance care planning is an imperative in ADRD care due to the long course of illness and its progressive and devastating effects on decision-making capacity. However, little attention has been directed at developing strategies to improve advance care planning for persons with ADRD and their family caregivers in primary care, which is the most common setting of initial diagnosis^{2,3} and ongoing medical management.^{4,5}

This study proposes to systematically develop and test a communication intervention, referred to as SHARE, to proactively engage family caregivers and normalize advance care planning in primary care. Our goal is to engage family caregivers in longitudinal interactions with primary care clinicians and stimulate and support advance care planning discussions in primary care. We focus on persons with mild, moderate, and severe cognitive impairment regardless of clinical diagnosis because of the importance of addressing

advance care planning early in the disease trajectory,^{6,7} the under-diagnosis of ADRD⁸⁻¹⁰ and because of the greater implementation potential of a protocol with broader applicability. We hypothesize that as compared with the minimally enhanced control care group, caregivers in the intervention group will report better quality of communication about end of life care with primary care clinicians at 6 months (primary outcome). We further examine the effects of the intervention on advance care planning processes (secondary outcomes) at 6 months. For patients who die by 24 months, we examine the quality of end of life care and bereaved family caregiver experiences with medical decision-making (secondary outcomes).

2.2 BACKGROUND

Alzheimer's Disease and Related Dementias (ADRD) are among the most profoundly disabling and costly of all health conditions¹¹ and the 5th leading cause of death.¹² Family caregivers are at the forefront of managing ADRD across the continuum of care. Clinicians rely on the substituted judgement of family for persons who lack decisional capacity toward the end of life.¹³⁻¹⁵ However, family caregivers are not routinely included in discussions about prognosis^{16,17} and are often poorly prepared to engage in surrogate decision-making.^{15,18,19} Compared to persons without ADRD, persons living with ADRD are less likely to complete an advance directive or formally designate a surrogate decision-maker,²⁰ placing them at heightened risk for unnecessary suffering and high utilization of burdensome and costly end-of-life care.²¹⁻²³

SHARE involves the following elements: 1) a letter from the practice introducing the initiative, to prepare persons and families to discuss goals of care,²⁴ 2) access to a designated staff member (e.g., medical assistant, social worker or nurse, lay person) trained to lead advance care planning discussions,²⁵⁻²⁷ 3) person-family agenda-setting, to align perspectives about the role of family and stimulate discussion about goals of care,²⁸ and 4) education about communication and available resources, including a 44-page brochure developed by the National Institute on Aging entitled "A Guide for Older People: Talking with your Doctor", a blank easy to complete advance directive, and facilitated registration to the patient portal (for patient **and** family), to extend electronic interactions and information access to family.^{29,30}

Each component has been found to improve a range of communication outcomes in other care contexts,²⁴⁻³⁰ but have not previously been applied in this combination or examined with regard to advance care planning in persons with cognitive impairment, as we propose. SHARE is designed to be broadly scalable and widely relevant to diverse primary care patients and stakeholders. Our study is timely in light of newly available Medicare billing codes for advance care planning discussions with non-physicians,³¹ recent recommendations of American Medical Association and National Quality Forum consensus committees emphasizing advance care planning in ADRD quality measurement,^{32,33} National Alzheimer's Project Act Goal 3.C. to expand assistance for families in planning for future care needs,³⁴ and recommendations from a 2016 National Academies of Sciences, Engineering, and Medicine report calling for strategies to proactively engage and support families in care delivery.³⁵

This study is guided by the patient-provider communication,³⁶⁻³⁸ family caregiving,^{39,40} health services,^{41,42} and health informatics^{43,44} literatures in acknowledging the multiple pathways by which interpersonal relationships influence treatment decisions and end-of-life care. We extend theory from the patient-provider communication literature^{37,45} to include participation of a family caregiver.³⁸ Engaging family in primary care is particularly important in dementia care because of the influential role of family in medical

decision-making,⁴⁶⁻⁴⁹ especially with disease progression at the end-of-life.⁵⁰⁻⁵² Our study seeks to improve communication for persons with cognitive impairment by establishing a structured protocol to proactively engage family caregivers in ongoing interactions with primary care clinicians and stimulate and support advance care planning in primary care throughout the disease trajectory. Our premise is that individuals and families expect clinicians to initiate advance care planning,⁵³ but that individual, family, and system factors including time, knowledge, and resources inhibit these conversations from occurring.⁵⁴ SHARE seeks to better equip persons with cognitive impairment and family caregivers with the knowledge, skills, and support to engage in effective communication and developing structured processes and enhancing capacity to engage in advance care planning. Our study is also guided by Normalization Process Theory, an applied theoretical model that articulates important contextual factors that promote or inhibit the routine incorporation of complex interventions into everyday practice.^{55,56} As Normalization Process Theory stipulates the importance of implementation and sustainability from the outset, we propose to qualitatively examine a range of process and contextual measures that could affect the design of a subsequent trial and subsequent diffusion of SHARE.

2.3 RISK/BENEFIT ASSESSMENT

2.3.1 KNOWN POTENTIAL RISKS

The interventions are unlikely to pose harm or discomfort any greater than that ordinarily encountered in daily life or in obtaining routine medical care. Patient involvement in the study includes agenda-setting, engaging in goals of care discussion, and survey completion. There is low potential that agenda-setting between persons with cognitive impairment and family caregivers may lead to disagreement or interpersonal conflict. Completing some of the survey measures about attitudes, quality of life, and end-of-care preparations may involve some psychological discomfort. Some participants may become uneasy or fatigued during the interview process or may become slightly agitated when interacting with a stranger or by being asked to respond to questions about their memory. Some participants may be upset by the prospect or experience of goals of care discussions. Also, there is a low possibility that despite all protections, subject privacy and/or confidentiality may be breached. We believe the likelihood of such risks is low, that we have considered these risks, and that we have adequate protections in place. Our prior work we have found that these experiences are relatively rare. The main risks of participating in this study involve inconvenience, personal time, the potential for becoming upset or fatigued, and potential loss of confidentiality. Participants will be free to terminate their participation at any time and will be reminded of this during the consenting process.

2.3.2 KNOWN POTENTIAL BENEFITS

It is anticipated that persons with cognitive impairment and family caregivers will experience more benefit than risk from participation in this study and that risks associated with participation are reasonable in comparison to knowledge that may be gained. Benefits accrued by intervention study participants may include greater clarity regarding the patient's health and treatment preferences and the communication roles to be assumed by family caregivers during face-to-face medical visits, in electronic interactions with primary care providers, and in future medical decision-making. In addition to improving advance directive completion we hypothesize that the intervention might improve medical visit communication and satisfaction with care. Societal benefits will result from this study. We will test a scalable protocol to improve the quality of communication about end of life care in primary care, extending knowledge regarding the implementation and effects of advance care planning for persons with cognitive impairment outside of institutional settings. If this trial has a positive effect on communication, the methodology has

broad potential application to improve advance care planning and end of life care in primary care. Participants in the minimally enhanced care group will not directly benefit from participation.

2.3.3 ASSESSMENT OF POTENTIAL RISKS AND BENEFITS

This is a Minimal Risk study of a behavioral intervention. The trial will be conducted in a population of older adults 80 years and older with cognitive impairment. The significance of our study rests in part on low completion of advance care planning in the target population despite high rates of mortality and adverse health events (e.g., hospitalization, emergency department visits). Advance care planning is already routinely offered in primary care and uptake of intervention processes will be at the discretion of patients and families. Based on our previous work and studies in this area by others, there is a small risk that participants will become anxious/agitated due to the prospect or experience of advance care planning. Adverse events that result from study participation are expected to be mild and psychological in nature. We will monitor rates of adverse health events by intervention group as a part of our analytic plan, but these events will not be systematically included in safety reporting as it is improbable that they will result from the intervention.

Individuals in the intervention and control groups may benefit from participation in this trial through improved communication between patients and caregivers, primary care providers, and family members regarding healthcare wishes, advance care directives, and the selection of decision makers for patient health. In addition, participants will benefit from the knowledge that participation in this trial may lead to improved outcomes for others in the future due to data gathered in this study. Potential societal benefits of this trial include a greater understanding of communication processes vital to advance care planning and a potential decrease in complicated or burdensome end-of-life care for older adults.

Several mechanisms to reduce the potential for psychological discomfort will be utilized. Interventionists and study interview staff will receive training in techniques for approaching older persons with cognitive impairment and family members, including sensitivity to discussing topics related to advance care planning and cultural competency for working with diverse populations. Intervention guides to help maintain these skills will be available as well as regular contacts, monitoring and feedback with the training team.

- This is a study about communication and ACP in primary care among older adults with cognitive impairment including ADRD. ADRD is a sensitive topic. Older adult participants will have a range of ADRD (from mild to severe) and not all older adults will be aware that they have ADRD or be in treatment for memory loss. Therefore, mention of cognitive impairment or ADRD in the recruitment materials or in the study title will be avoided.
- It will be emphasized in training interventionists that advance care planning is voluntary for patients, and that advance care planning sessions should not be initiated or be terminated if patients are not interested or do not wish to continue at that session.
- While it is possible that agenda-setting or advance care planning may introduce tension in the patient-caregiver relationship by acknowledging the distinct perspective of each individual, study staff will seek to mitigate associated risks by preparing interviewers and interventionists to anticipate concerns and mediate difficult discussions.
- Caregivers of older persons with significant health conditions, including those with Alzheimer's Disease and Related Dementias, are at heightened risk of depression and anxiety. During regular assessment for this study, participants will be screened for depressive symptoms or anxiety. Patients will be notified of scores above a pre-determined threshold and will be asked if they would like an educational brochure about depression or anxiety (as appropriate), or if they would like the

interventionist to notify the family's primary care clinician of this finding. Caregivers will also be encouraged to follow-up to discuss this with their health care clinician.

- In the event of extreme psychological discomfort among intervention patients or caregivers, interviewers and interventionists will be trained in procedures for ensuring necessary medical or professional intervention. Referral resource(s) will be identified for distressed family members within each health system. Primary care patients will be referred to their primary care clinician. Caregivers will be referred to the health system referral resource or to medical or psychological care (e.g., counseling, support, advocacy) as appropriate.

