Existing asynchronous secure messaging features of the patient portal enable patients and individuals who have shared access to contribute to the electronic health record (e.g., to elaborate on meeting discussions, communicate emerging concerns, or summarize informal family conversations) to inform and stimulate ongoing discussions and documentation. This feature may be leveraged in communications with the interventionist. At the initial meeting the interventionist will clarify ongoing availability for follow-up meetings and seek patient and family input regarding the frequency (e.g., monthly, quarterly) and mode (by phone, via secure electronic messaging through the patient portal) of future “check-in” contacts to assess interest in scheduling future meetings. Subsequent in-person, telephone, or video conference meetings will occur as a result of “check-in” contacts initiated by the interventionist, ad-hoc requests by persons and/or family caregivers, or notable changes in health (e.g., unplanned hospitalization or emergency department visit, or notable change in health or function). SHARE interventionists will be expected to document the occurrence, content, and outcomes of advance care planning conversations after each ACP conversation (E5).

Participants may be asked to complete a brief questionnaire following all interventionist/facilitator meetings about their satisfaction with the conversation and their perception of its importance (E6, E7). Participants will be given the survey via web survey link or as a mailed paper form with a pre-addressed (to the study office or PI’s home address), stamped envelope return to the study team once completed.

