8.3 ADVERSE EVENTS AND SERIOUS ADVERSE EVENTS

8.3.1 DEFINITION OF ADVERSE EVENTS

We follow the Office of Human Research Protections' guidance in our approach to defining and identifying Serious Adverse Events, Adverse Events, and Unanticipated Problems. **Adverse events** are any untoward or unfavorable medical occurrence, including any abnormal sign, symptom, or disease identified by any member of the research team that may occur at any time following consent of participants whether or not it is considered related to participation in the research. Advance care planning is already routinely offered in primary care and uptake of intervention processes will be at the discretion of patients and families. Based on our previous work and studies in this area by others, there is a small risk that participants will become anxious/agitated due to the prospect or experience of advance care planning. Adverse events that result from study participation are expected to be mild and psychological in nature. Interventionists will be trained to monitor, record, and manage such events and make effective referral.

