8.3.2 DEFINITION OF SERIOUS ADVERSE EVENTS

Serious adverse events are any adverse event temporally associated with research participation that: 1) results in death; 2) is life-threatening; 3) requires inpatient hospitalization or prolongation of existing hospitalization; 4) results in a persistent or significant disability/incapacity; 5) results in a congenital anomaly/birth defect; or 6) any other adverse event that, based upon appropriate medical judgment, may jeopardize the subject's health and may require medical or surgical intervention to prevent one of the other outcomes listed in this definition. This is a minimal risk behavioral intervention and we do not anticipate any serious adverse events. The trial will be conducted in a population of older adults 80 years

and older with cognitive impairment and the significance of our study rests in part on low completion of advance care planning in the target population despite high rates of mortality and adverse health events (e.g., hospitalization, emergency department visits). We will monitor rates of serious adverse events by intervention group as a part of our analytic plan, but these events will not be systematically included in safety reporting as it is improbable that they will result from the intervention. If any deaths should occur, they will be reported by the principal investigator to the DSMB and National Institute on Aging Program Officer within 24 hours of initial notification.

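### Adverse event rates are to be viewed by group with no common-source rule, although facilitator contacts that can bring events to light exist only in SHARE

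*Combined protocol and SAP*

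**What the plan says.** Two sections promise event rates by arm. Section 2.3.3 does so for adverse health events, giving hospitalization and emergency department visits as examples: "We will monitor rates of adverse health events by intervention group as a part of our analytic plan". Section 8.3.2 does so for serious adverse events: "We will monitor rates of serious adverse events by intervention group as a part of our analytic plan". Both add that these events will not be included systematically in safety reporting.

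How events come to be recorded is spread over several places:

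- **Definition (8.3.1).** Adverse events are those "identified by any member of the research team that may occur at any time following consent of participants", whether or not they are related to the research.
- **Schedule (1.3).** The row reads "Adverse Events | | X | X | X | X | X | X | X". The third mark falls in the column headed ACP and patient portal use. The others fall at enrollment, randomization, 6, 12 and 24 months, and bereavement.
- **Facilitators (8.3.1).** "Interventionists will be trained to monitor, record, and manage such events and make effective referral".
- **Facilitator contact (6.1.2).** At the first meeting the facilitator will "seek patient and family input regarding the frequency (e.g., monthly, quarterly) and mode" of later check-ins. Further meetings may follow check-ins, requests from the dyad, or "notable changes in health (e.g., unplanned hospitalization or emergency department visit, or notable change in health or function".
- **Controls (6.1.1, 6.1.2).** A letter, a brochure and a blank advance directive, with no facilitator.
- **Common follow-up (8.1, 10.1.9.1).** Adverse events are among the items collected at the follow-up and bereavement assessments in both arms. These are conducted by masked staff.

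Section 9.4.4, Safety Analyses, is marked not applicable.

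**The concern.** A comparison of event rates between arms is interpretable only if both arms have the same chance of having an event recorded. Here one arm has an additional route. SHARE dyads speak with an unmasked facilitator at one or more ACP meetings and at check-ins, and some of those contacts are prompted by the very hospitalizations and emergency visits that section 2.3.3 names. Between randomization and bereavement, the scheduled contacts that controls share are the surveys at 6, 12 and 24 months.

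If events learned of through facilitators enter the by-group rates, SHARE could show more events than control when the true rates are equal. Two misreadings then become possible: a false safety signal, or a genuine excess dismissed as better detection. The Data and Safety Monitoring Board (DSMB) is a likely reader of such figures, because it receives a listing of all adverse events twice a year (8.3.5) and may see unblinded data (5.5.3, 6.3).

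**Working it through.** The documents state no adverse event rate, capture rate or safety power, so there is no figure of the plan's own to reproduce. The check has two parts.

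**1. Routes by which an event can be recorded**

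| Route | SHARE | Control |
|---|---|---|
| Enrollment and randomization (1.3) | yes | yes |
| 6-, 12-, 24-month and bereavement surveys (1.3, 8.1) | yes | yes |
| ACP meetings (1.3, 6.1.2) | yes | no |
| Facilitator check-ins (6.1.2) | yes | no |
| Meetings after hospitalization or emergency visit (6.1.2) | yes | no |
| Electronic health record (EHR) and CRISP, the state health information exchange (10.1.9.1) | named only for advance directives, portal use and burdensome care | same |

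The ACP column also covers portal use, which is extracted from records in both arms. The facilitator contact within it is SHARE-only. The broad definition in 8.3.1 does not exclude an event that a facilitator learns of, and no section separates such events from the by-group rates.

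**2. Direction and illustrative size**

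Let the true event rate *r* be equal in both arms, let *s* be the proportion captured by the common sources (assumed the same in both arms), and let *t* be the proportion captured by common sources plus facilitators. Then

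apparent rate ratio = (*r* × *t*) / (*r* × *s*) = *t* / *s*.

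An added route cannot lower capture, so *t* ≥ *s* and the ratio is at least 1. All values of *s* and *t* below are assumptions.

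| *s* | *t* | *t* / *s* |
|---|---|---|
| 1.00 | 1.00 | 1.00 |
| 0.90 | 0.92 | 1.02 |
| 0.70 | 0.80 | 1.14 |
| 0.70 | 0.90 | 1.29 |

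The last row requires facilitators to find (0.90 − 0.70) / (1 − 0.70) = 0.67, or two thirds, of the events the surveys miss. The ratio is sensitive to *s*: with *s* = 0.50 and facilitators finding half of what is missed, *t* = 1 − 0.50 × 0.50 = 0.75 and the ratio is 1.50. The documents set no upper bound.

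If only common sources are counted, *t* = *s* and the ratio is 1.00 whatever *s* is.

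**The case against.** Several points on the other side are sound.

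- **What facilitators record.** In 8.3.1 the sentence on facilitators follows text about anxiety, agitation and mild psychological events, so it refers most directly to distress from ACP. The link in 6.1.2 between a hospitalization and a further meeting is a scheduling trigger. That facilitators would be the source of hospitalization or emergency visit counts is an inference from the broad definition and the ACP-column mark.
- **The source is not named.** Section 8.2 refers safety monitoring to a Data and Safety Monitoring Plan and a Manual of Procedures, which are not among the documents. Masked staff already extract EHR and CRISP data (10.1.9.1), and 9.4.3 describes CRISP as covering all hospital encounters. A symmetric source may be intended.
- **Consequences are limited.** The rates are descriptive, the events stay out of systematic safety reporting, and no interim analysis is planned (9.4.6).
- **Exposure may be modest.** The aim is at least one ACP discussion per dyad (6.4), dyads may decline all activities (7.1), and monthly or quarterly check-ins are only examples.

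Three stronger readings are tempting and are not supported. A reader might infer that SHARE *will* show an excess; since the source of the rates is unstated, *could* is the most the text allows. A reader might turn the ratios into a probability of a falsely significant excess; that would be the error rate of a test the plan does not contain, at an event rate it does not give. A reader might say controls can report events only at surveys; the schedule also marks enrollment and randomization, the any-team-member definition applies to both arms, and the 24-hour rule for deaths (8.3.2) does not depend on arm.

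What remains is that nothing in the documents restricts the promised rates to common sources, while an extra route exists in one arm only.

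**Conclusion.** The concern holds as a risk of ascertainment bias in a descriptive comparison. Applied as written, the definition and schedule allow facilitator-found events to enter by-group rates that have no counterpart in control, and any resulting bias runs towards apparent harm from SHARE.

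The direction rests on survey capture being equal in the two arms. The size rests wholly on assumed capture: no bias if common sources are complete, and an apparent ratio of about 1.3 at 70% against 90%. It would be nil for any event type taken entirely from records in both arms. The primary endpoint is unaffected. The point merits a change because the rates are promised in two places and the remedy is cheap.

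**What to change.** Add a short rule under 9.4.4, cross-referenced from 2.3.3 and 8.3.2:

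1. By-group event rates count only events ascertained the same way in both arms: the same questions at the 6-, 12- and 24-month and bereavement surveys and, for hospital encounters, EHR/CRISP extraction by masked staff over the same period in both arms.
2. Facilitator-detected events, including distress related to ACP, go in a separate SHARE-only table, labelled as having no control counterpart. This keeps visible the harm the protocol expects.
3. All events, from whatever source, still go to individual safety review and to the DSMB listing, with the source of detection recorded.

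The cost is wording, a source field, and some additional extraction, because the record sources are at present named only for other measures. The by-group table will hold fewer events, and its survey part relies on recall over up to 12 months, but that limitation falls on both arms alike.
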